After checking in with facility patient-care staff to confirm the availability of the potential participant, patients who appear appropriate per chart will be approached by WU research staff and told that they may be eligible for the enhanced rehabilitation study. To ensure participants' comfort, the study team will assess the setting and ensure that the individual is positioned such that they can comfortably complete any assessments, including writing in a reasonable position, that they have had an opportunity to go to the toilet, eat and are dressed (if appropriate). Just asking the participant may not be the best approach for all individuals as some may agree without actually feeling this it is the best time or situation. It is important that participants not put off their own needs (whether it be repositioning themselves, using the bathroom or getting dressed) and that the research assessments not interfere with this.

If the patient gives their assent, research staff will screen them for cognitive impairment, with the Short Blessed Test (SBT). If they do not assent to the screening then we will not ask them the questions and will not contact them further.

Patients who score 13 or higher will be assumed unable to provide consent and thus will be excluded from the study. Study staff and/or PI will use clinical judgment to determine whether to include patients who score between 10 and 12 on the SBT. If they are not cognitively impaired (score 0-9 on SBT) at the time of this screening we will go through the full informed consent process for the study.

Research staff will review the consent form with the patient in their room at the skilled nursing facility, encouraging the patient to ask questions throughout. The assessment of understanding tool will be used as needed to ensure each patient understands the procedures, risks, and benefits of the study.

2.d Randomization Method and Blinding

We will randomize 1:1 to EMR (i.e., all OT/PT sessions done by EMR-trained and supervised therapists) or SOC (i.e., all sessions done by non-EMR-trained therapists), as in our pilot RCT. We will stratify by SNF site and by baseline depression status. To prevent subversion of randomization,⁶¹ the statistician will hold the randomization list, releasing an assignment once a participant is consented and eligible.

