
Our sample size is based on 80% power to detect a Cohen's $d=0.4$ effect size on the ANCOVA difference in treatments at day 21, based on a two-tailed $p<0.025$ (because two outcome measures are used). G*Power 3.1.2 was used for power calculations. A Cohen's $d=0.4$ is between "small" (0.2) and "medium" (0.5) effect sizes. Effect sizes for function were in the "large" range, $d=0.7-0.9$, but we acknowledge that these observed

effect sizes are qualified by the small sample size, and it makes most sense to be more cautious regarding likely effect sizes in a full-scale study, hence our choice to power at $d=0.4$. Such an effect size is clinically relevant for the functional outcomes.³ *We will only examine affective recovery as an outcome for those who are “affectively impaired” to begin with; i.e., those with clinical depression at baseline; with this reduced N, we are powered at 80% for a $d=0.54$. This same power analysis would apply for any subgroup analysis of depressed; i.e., if we wish to demonstrate that EMR is effective both in the case of clinical depression and in “non-depressed” older adults.*

G2 Interim Monitoring and Early Stopping

Not applicable; we do not have any interim data analysis or early stopping plans.

G3 Analysis Plan

The continuous demographic and clinical variables at baseline will be compared between the EMR group and the SOC group using the Two Independent Sample t Test or the Wilcoxon Two Sample Test, whichever is appropriate. Baseline categorical variables (e.g., race) will be compared between the groups using either the Chi Square Test or Fisher’s Exact Test, whichever is appropriate. We will examine data descriptively using crosstabulations, histograms, and tests for normality (with corrective actions, data transformation or nonparametric alternatives, as needed). An analysis-appropriate technique will handle missing data.

G4 Statistical Methods

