Time course analyses will be conducted to investigate the differences between pre and post outcome measures. These analyses will be used to ascertain whether there is a statistically significant difference in change over time between the EMR group and the SOC group, controlling for baseline values. Analyses of the outcome measures for normality will be carried out. Time course analysis techniques such as mixed effects models, t test of the differences, Wilcoxon test of the differences, or ANCOVA on the differences (using baseline value as the covariate) will then be conducted, depending on the normality tests. Our favored method for the primary analysis of baseline to day 30 (i.e., pre-post treatment) effects is the ANCOVA approach, comparing the EMR and standard-of-care groups in change scores, covarying for baseline scores. This approach is recommended as the superior and most well-powered approach for examining pre-post RCT data.⁹¹ Our tests of the pilot data agreed with this: the ANCOVA approach had as much or more statistical power than other approaches (t-test, Wilcoxon, mixed-effect model) for all outcomes.

Participants will be randomized within each facility (i.e., stratified by facility) and then receive a PT/OT therapist pair who either is or is not trained/supervised in EMR based on randomization assignment. Thus participants are nested within therapists and therapists are nested within facilities. This multi-stage nested (hierarchical) design structure introduces possible correlation of participant outcomes with therapist. Such classification effects (facility/therapist) will be analyzed using Proc Nested in SAS or with the multi-level modeling available in Mplus that deals with stratification, clustering, and weighting.

We will also examine all time points to Day 90, to provide a real-world estimate of EMR and improve power to detect important secondary outcomes such as rehospitalization and institutionalization. We acknowledge these data may become somewhat naturalistic

in a rehabilitation population, given differences in length of stay, transfers to different facilities, and re-hospitalizations. Mixed effects models are the preferred method for these multiple-time-point analyses, especially as some missing data are to be expected post-discharge.⁹²

H Data Handling and Record Keeping

H1 Confidentiality and Security

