Explanation: The purpose of H1 is to examine the effectiveness of EMR. If H1 is supported, this could establish EMR as the gold-standard practice for post-acute rehabilitation. Our primary analysis is the change from baseline to Discharge. This single primary endpoint allows for an effectiveness test that is not confounded by length of stay differences or post-discharge issues beyond the reach of EMR.

2. Aim 2: Examine EMR's ability to overcome patient-level barriers to successful rehabilitation.

H2: The effectiveness of EMR for functional recovery will be greatest in: (a) patients with clinical depression; (b) patients with high levels of medical comorbidity; (c) patients with cognitive impairment.

Explanation: EMR was designed to overcome barriers to rehabilitation (for example, due to depression); therefore, the difference in functional recovery between EMR and SOC should be greater in the most vulnerable older adults. If H2 is supported, we will demonstrate that older adults with these common comorbidities benefit the most from high intensity, high engagement rehabilitation. If so, this would refute conventional wisdom in post-acute rehabilitation, codified in admission criteria for rehabilitation facilities, regarding the appropriate candidates for rehabilitation (as described in Significance).

3. Aim 3 (Secondary): Effect of EMR on MADRS scores on individuals with clinical depression.
4. Calculated a rate of clinical depression (SCID for those with elevated MADRS score):

22 participants had the SCID administered.

8 did not have depression diagnosis while 14 did have depression diagnosis.

Conclusion: only 14 individuals in the study had a clinical depression (ie, a diagnosis of depression). No further analyses to be done.

Additional Variables/Outcomes

6-Minute Walk/Gait Speed: Administered at Baseline and Discharge. Two components for 6-Minute Walk:

- 1) Distance Ambulated (feet): text box. If unable to complete, distance was entered as a 0.
- 2) Time: options are 6 minutes, Other time (MM:SS), and N/A

Two components for Gait Speed (Baseline, Day 30, Discharge):

- 1) Distance: radio button (10 meters, 4 meters, 0 meters). If unable, 0 meters selected.
- 2) Time (seconds): text box (if unable, time is 0).

Disposition (i.e., discharge to community vs. not)

Rehospitalization (rate).

Secondary analyses (not for main paper):

1. PANAS (A positive and a negative affect score).

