2. PROMIS (Ability to Participate in Social Roles and Activities).
3. OARS IADL.

Process data: Measures of the dosage of intervention (# of EMR steps done in each therapy activity; PAT %; Rehab Participation Scale Score) before and after training.

Study Methods:

i. Trial Design:

This was a randomized, parallel-group trial where patients received either EMR or SOC therapy.

Patients who received EMR received therapy only from therapists who were trained and supervised in EMR. Their therapy sessions followed the EMR protocol. Otherwise, their SNF care did not differ from usual care.

Patients who received SOC received therapy only from PT/OTs (or assistants) who were not trained nor supervised in EMR. These therapists were monitored (videotaped or observed) but were not asked to do anything differently with their patients.

ii. Randomization:

Randomization (blocks...2 and 4 patients). was 1:1 to EMR or SOC with stratification by SNF site and by baseline depression status.

iii. Sample Size:

The sample size was based on 80% power to detect a Cohen's $d=0.4$ effect size on the ANCOVA difference in treatments at primary endpoint, based on a two-tailed $p<0.025$ (because two outcome measures are used). G*Power 3.1.2 was used for power calculations. A Cohen's $d=0.4$ is between "small" (0.2) and "medium" (0.5) effect sizes. Effect sizes for function were in the "large" range, $d=0.7-0.9$, but we acknowledge that these observed effect sizes are qualified by the small sample size, and it makes most sense to be more cautious regarding likely effect sizes in a full-scale study, hence our choice to power at $d=0.4$. Such an effect size is clinically relevant for the functional outcomes. *We will only examine affective recovery as an outcome for those who are "affectively impaired" to begin with; i.e., those with clinical depression at baseline; with this reduced N, we are powered at 80% for a $d=0.54$. This same power analysis would apply for any subgroup analysis of depressed; i.e., if we wish to demonstrate that EMR is effective both in the case of clinical depression and in "non-depressed" older adults.*

iv. Statistical Interim Analyses/Stopping Guidance:

Not applicable; we did not have any interim data analysis or early stopping plans.

v. Timing of Final Analysis:

All outcomes will be analyzed collectively.

vi. Timing of Outcome Assessments (including windows):

	Schedule of Assessments	SNF admit (baseline)	Day 7	Day 30	SNF discharg e	Day 60	Day 90

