Outcomes	Function						
	Barthel Index (primary outcome)	X		X	X	X	X
	Gait speed	X		X	X		
	6-minute walk	X			X		
	Depression SCID (given if indicated by MADRS)	X					
	MADRS	X		X			
	17-item positive and negative affect scale	X	X	X		X	X

Processes	Rehabilitation intensity					
	Patient active time & actigraphy (at 20% of sessions at random)	collected each session throughout stay				
	Treatment engagement					
	Observer-rated Rehabilitation Participation Scale (at 20% of sessions at random)	collected each session throughout stay				
	Fidelity data (at 20% of session at random)	collected each session throughout stay				
	Post-Treatment Affect					
	Self-Assessment Moniker (at 20% of session at random)	collected each session throughout stay				
	Patient Satisfaction and Treatment Fidelity Survey	Collected after therapy sessions				
	Other rehabilitation variables					
	Rehospitalization		X	X	X	X
	Disposition (home, long-term care)	X	X	X	X	X
	Social Participation (PROMIS Ability to Participate in Social Roles and Activities)				X	X
	Instrumental Activities of Daily Living (OARS IADL)				X	X
	Executive Functioning (Clock Drawing Test)	X				
	Fear of Falling	X				
	Readiness for Rehab	X	X			
	Short Blessed Test	X				
	Medical Comorbidity (CIRS-G)	X				
	Barthel Index: Pre-morbid version	X				

Statistical Principles:

i. Confidence Intervals and P-Values

Level of significance is 5%

ii. Adherence and protocol deviations

Protocol Deviation:

Any alteration or modification to the IRB-approved research without prospective IRB approval. The term research encompasses all IRB-approved materials and documents including the detailed protocol, IRB application, consent form, recruitment materials, questionnaires/data collection forms, and any other information relating to the research study.

Therapist adherence and competence was tracked two times per participant.

Variables: number of EMR principles used per therapy session; PAT.

iii. Analysis Populations

Trial Population:

- i. Screening data to describe representativeness of trial sample will include age, gender, race and ethnicity.
- ii. Eligibility

Inclusion Criteria:

- a. 65 years of age and older
- b. Admitted to a skilled nursing facility for post-acute care from PT and OT for 2 weeks or more.

Exclusion Criteria:

- a. Language, visual or hearing barriers to participation (e.g. unable to communicate with research staff).

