The secondary analyses for Six-Minute Walk distance and Gait Speed will use a Mann-Whitney U Test to test for differences in means between groups. In addition, a Chi-Square test will be employed to test for independence between condition and the secondary outcome variable re-hospitalization. Finally, the outcome of self-reported function will use a marginal model using time (30, 60, and 90 days), condition and time x condition as fixed effects, with a covariance structure specified based on BIC.

Exploratory analyses will also test whether the effects of age, gender, race and site (i.e., Barnes Jewish Extended Care Vs Alexian Brothers Sherbrooke Village) altered the conclusions of the primary results as well as the conclusions of the moderator results.

Note: we will not look at the nesting of subjects within therapists who are then nested within site as this is not possible due to the inconsistency of assigning therapists to participants.

iii. Missing Data

We use a marginal model which accounts for missing data (no multiple imputation was used).

iv. Harms

An adverse event (AE) is any untoward medical occurrence in a subject temporally associated with participation in the clinical study or with use of the experimental agent being studied. An adverse finding can include a sign, symptom, abnormal assessment (laboratory test value, vital signs, electrocardiogram finding, etc.), or any combination of these.

AEs will be labeled according to severity (i.e., mild, moderate or severe), which is based on the AE's impact on the participant.

AEs will be categorized according to the likelihood that they are related to the study intervention or other study procedures (i.e., definitely unrelated, definitely related, probably related, or possibly related).

SAEs that are unanticipated, serious, and possibly related to the study intervention will be reported to the IRB, and NIMH in accordance with requirements. Unexpected fatal or life-threatening AEs related to the intervention will be reported to the NIMH Program Officer within 7 days. Other serious and unexpected AEs related to the intervention will be reported to the NIMH Program Official within 15 days. Anticipated SAEs will be handled in a less urgent manner but will be reported to the IRB in accordance with their requirements.

v. Statistical Software

All analyses will be performed using SAS and/or R.

vi. References

none

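### Rehospitalisation is compared with a pooled chi-square test although randomisation was stratified, and no between-arm contrast or confidence interval is specified

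*SAP*

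**What the plan says.** - **Test.** SAP, Analysis Methods: "a Chi-Square test will be employed to test for independence between condition and the secondary outcome variable re-hospitalization". No stratum, covariate, effect measure or interval is attached to it.
- **Randomisation.** SAP, Study Methods, Randomization: allocation "was 1:1 to EMR or SOC with stratification by SNF site and by baseline depression status", in blocks of 2 and 4. Protocol section 2.d (Randomization Method and Blinding) agrees: "We will stratify by SNF site and by baseline depression status".
- **Summary measure.** SAP, Additional Variables/Outcomes: the entry reads "Rehospitalization (rate", with the bracket then closed. It gives no contrast between arms. The SAP item on confidence intervals and p-values sets only a 5% significance level.
- **Where site is used.** SAP, Analysis Methods: site enters only exploratory checks of the primary and moderator results. Rehospitalisation is not covered.
- **Standing of the outcome.** Protocol G4 wants to examine all time points to Day 90, in part to "improve power to detect important secondary outcomes such as rehospitalization and institutionalization".
- **Depression.** SAP, Objectives: only 14 participants had a depression diagnosis.
- **Disposition.** The SAP lists it as an outcome, but Analysis Methods names no test for it.

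**The concern.** When allocation is balanced within strata that predict the outcome, the true sampling variance of the difference between arms contains only within-stratum variation. A pooled 2x2 table estimates that variance from the overall event rate and so also counts the variation between strata. The standard error is then too large and the test rejects too seldom. Analysing by the strata already used in randomisation removes this at no cost.

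Reporting is the other half. A test of independence gives a p-value but no size of effect. The trial was sized for a standardised difference of 0.4 on the ANCOVA comparison, not for rehospitalisation, so a non-significant result here could easily reflect too little information. Without an interval for a named contrast, the reader cannot tell that from no effect.

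**Working it through.** The documents give no event rate, target effect or power for rehospitalisation, so there is no figure of the plan's own to reproduce.

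**Inputs from the documents.** 252 participants (Protocol, opening summary of aims), 1:1, hence 126 per arm; two facilities (Protocol J1; SAP, Analysis Methods); 5% level (SAP, Statistical Principles), taken as two-sided.

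**Assumptions.** Equal site sizes (63 per arm per site), a common odds ratio of 0.5, no missing outcomes, and control-arm site rates averaging 25% with a varying gap between sites.

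**Step 1: how conservative is the pooled test under the null?** With site rates p1 and p2 and mean p:

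- variance used by the pooled test: p(1 − p)
- variance that applies: [p1(1 − p1) + p2(1 − p2)]/2
- ratio R = second/first; the effective critical value is 1.96/√R.

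At 15%/35%: pooled 0.25 × 0.75 = 0.1875; within-site (0.1275 + 0.2275)/2 = 0.1775; R = 0.947; √R = 0.973; critical value 2.014; true two-sided level 4.4%.

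At 10%/40%: within-site (0.09 + 0.24)/2 = 0.165; R = 0.88; √R = 0.938; critical value 2.089; true level 3.7%.

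**Step 2: power.** The stratified test is Cochran-Mantel-Haenszel. In site k, let a be EMR events, m all events, n1 and n0 the arm sizes and N = n1 + n0. The statistic is [Σ(a − n1·m/N)]² / Σ[n1·n0·m(N − m)/(N²(N − 1))], referred to chi-square on 1 degree of freedom. The pooled test is the uncorrected Pearson chi-square. Each setting was simulated 200,000 times, so each power figure has a Monte Carlo error of about √(0.5 × 0.5/200,000) = 0.1 points.

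| Control rates by site | Level, pooled (Step 1) | Power, pooled | Power, stratified | Gain (points) |
|---|---|---|---|---|
| 25% / 25% | 5.0% | 57.3% | 57.4% | 0.1 |
| 20% / 30% | 4.8% | 56.4% | 57.1% | 0.7 |
| 15% / 35% | 4.4% | 54.0% | 56.0% | 2.0 |
| 10% / 40% | 3.7% | 49.8% | 54.2% | 4.4 |

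The simulated null rejection rates match the Step 1 levels to within 0.1 points for the pooled test and lie between 4.9% and 5.1% for the stratified test. A separate run of 20,000 trials per setting gave 49.7% and 54.0% in the last row, a gain of 4.3.

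**Step 3: the depression stratum.** Fourteen diagnosed participants over two sites and two arms is 14/4 = 3.5 per cell. In 20,000 trials with site rates of 15%/25% and an assumed 40% in those 14, stratifying by both factors raised power from 49.1% to 50.5%. With site alone at 15%/25%, the change was 48.2% to 49.3%. The depression stratum adds almost nothing if that diagnosis defined it.

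**Step 4: what an interval would show.** Take a control rate of 25% and an odds ratio of 0.5. The EMR odds are 0.5 × 0.25/0.75 = 0.1667, a risk of 14.3%, so the risk difference is 10.7 points. Its standard error is √[(0.25 × 0.75 + 0.143 × 0.857)/126] = 0.0496, and the 95% half-width is 1.96 × 0.0496 = 9.7 points. Since power is between about 50% and 57% throughout the table, a non-significant p-value would be nearly as likely as a significant one even with the odds halved.

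**The case against.** The planned test is valid, and the precision argument depends on an assumption that the documents cannot confirm: no passage gives rehospitalisation by site or says that the facilities differ. With equal site rates the gain is nil, and a gain above about 2 points needs something like a fourfold gap between sites. All of this stands.

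Three stronger readings are tempting but unsupported. A reader might infer that ignoring the strata invalidates the test or inflates type I error; Step 1 shows the reverse. A reader might infer that the pooled test is less precise in any event; it is so only if site or depression predicts the outcome. A reader might infer that no effect will be visible at all; but the SAP lists a rate, and if rates are shown by arm a crude difference follows by subtraction. What is missing is a named contrast with an interval.

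It can also be said that G4 seeks its power from using all time points to Day 90, with mixed models preferred, and not from a stratified table. That is true, so G4 shows that the outcome matters but does not prescribe this method. Nor does the SAP say which scheduled assessment (Day 30, discharge, Day 60 or Day 90) the test uses. That is a further gap in the same sentence, and it does not remove this one. Finally, the SAP is marked final and already reports study counts, so any change is late and must be declared as such.

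**Conclusion.** The point holds as a minor, free improvement. The analysis of rehospitalisation does not use the site strata built into the randomisation, and no contrast or confidence interval is specified. Under the assumptions above, the cost in power is between nothing and about 4 points, and most likely towards the low end unless the facilities differ widely. Unequal site sizes, missing outcomes or a different odds ratio would shift these figures. The missing interval is the more useful half, because it does not depend on whether site is prognostic. The primary conclusion on the Barthel Index is unaffected.

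**What to change.** In SAP Analysis Methods, replace the chi-square test for rehospitalisation with a Cochran-Mantel-Haenszel test stratified by site, adding the depression stratum only where cell counts allow. State that event rates by arm will be reported with the site-stratified risk difference or odds ratio and its 95% confidence interval. Name disposition in the same sentence, since it has no test at present. The edit is also the place to name the assessment window.

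Record the change with its date as a departure from the final SAP, and say whether outcome data by arm had been seen. The cost is one or two sentences and a few lines of code in the software already named (SAS or R), with no new data.

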Therefore, we created Enhanced Medical Rehabilitation (EMR) for older adults. A real-world adaptation of the science of behavior change, EMR is an integrated set of skills for physical and occupational therapists (PT/OT) that transform standard post-acute rehabilitation through: (1) a patient-directed, interactive approach (2) increased rehabilitation intensity (3) frequent feedback to patients on effort and progress. We developed training and supervision techniques so that PT/OTs carry out these skills with high treatment integrity.

In NIMH R34 pilot work, we found: (1) EMR is high-intensity and engaging: therapy by PT/OTs trained and supervised in EMR is greatly amplified in intensity and patient engagement compared to standard-of-care rehabilitation. (2) EMR improves functional and affective recovery: patients randomized to EMR had better improvement of function, physical performance, and positive and negative affect. (3) EMR overcomes barriers to rehabilitation: patients with depressive symptoms, cognitive impairment, and multiple medical comorbidities benefitted most from EMR relative to standard therapy.

We propose a randomized trial that will test EMR's benefits over standard-of-care rehabilitation for affective and functional recovery. Our aims are (1) examine the effectiveness of EMR for improving functional and affective outcomes in 252 older adults admitted to SNFs for post-acute rehabilitation, and (2) examine EMR's ability to overcome patient-level barriers (such as depression) to successful rehabilitation.

The innovation of this project is high: it is a novel application of theories of behavior change to improve both affect and function. It responds to NIMH strategic plan objective 3, "Develop new and better interventions for mental disorders that incorporate the diverse needs and circumstances of people with mental illness."

The public health significance is also high: recovery from disablement is a health issue of enormous human and economic significance. Success in this line of research will make rehabilitation more effective. Doing so would benefit all older adults in this sector of care but particularly those with depression, cognitive impairment, and other complications. This project addresses NIMH's goal of interventions to improve mental health and related health outcomes in real-world settings.

A2 Study Aims and Hypotheses

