Procedures designed to maintain confidentiality include: (1) formal training sessions for all research staff emphasizing the importance of confidentiality; (2) specific procedures developed to protect subjects' confidentiality, and (3) formal mechanisms limiting access to information that can link data to individual subjects. Data forms that include identifying information will be kept in locked cabinets. Only the unique ID number, assigned by the research coordinator at the time of initial contact will represent subjects during data entry, data transfer, data analysis, or other file management procedures. To facilitate tracking, a password-protected computer file will be maintained containing the identity of subjects, their ID numbers, and information about how they can be reached. This file, however, will contain no clinical data. Only members of the investigative group will have access to secured files or to master lists for subject code numbers and will be well informed regarding the protection of patients' rights to confidentiality. Identities of participants will not be revealed in the publication or presentation of any results from this project.

Videotaping permission and confidentiality: subjects will be videotaped for the purposes of observing the therapists and providing training material. Subjects will sign a consent which indicates the use of the videotaping, who may have access to the videotaping, and the length of time that the videotape will be kept by investigators. Videotapes will be kept with the same confidentiality procedures as other research data.

H2 Training

All research staff will receive standardized training in privacy and confidentiality. All research staff will be thoroughly trained on study procedures and assessments. Raters will role play assessments with supervisors. New raters will be observed by their supervisors before conducting assessments independently.

Therapists at partnering facilities interested in delivering the study intervention will receive training in human subjects research in accordance with the Washington University policy. They will also participate in initial and ongoing training in the study intervention.

H3 Records Retention

Records will be kept from all consented participants. De-identified information will be kept on excluded participants, limited to age, gender, race, and reason for exclusion.

I Study Monitoring, Auditing, and Inspecting

I1 Study Monitoring Plan

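### The SAP drops the planned therapist-clustering analysis with no substitute; if Barthel change varies by therapist, the primary standard error is too small

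*SAP*

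**What the plan says.** **Delivery.** Protocol E2 2.d defines the EMR arm as "all OT/PT sessions done by EMR-trained and supervised therapists" and the SOC arm as the reverse. SAP Study Methods i repeats that each arm was treated only by its own therapists. Protocol H2 describes those to be trained as "Therapists at partnering facilities interested in delivering the study intervention", so the EMR set is at least partly self-selected.

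**Planned handling.** Protocol G4 describes participants within therapists within facilities and says: "This multi-stage nested (hierarchical) design structure introduces possible correlation of participant outcomes with therapist". It commits to analysing these effects with nested or multilevel software.

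**Current handling.** The Note in SAP Analysis ii states that nesting will not be examined, "as this is not possible due to the inconsistency of assigning therapists to participants". No other model, clustered variance or sensitivity analysis replaces it. The primary model contains time (baseline, discharge), condition and their interaction, with a covariance structure chosen by BIC. Site appears only as an exploratory covariate.

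**Sample size.** SAP Study Methods iii gives "80% power to detect a Cohen's $d=0.4$ effect size on the ANCOVA difference in treatments at primary endpoint", at two-sided 0.025. It mentions no ICC, therapist count or design effect, and neither does Protocol G1.

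**The concern.** Randomising participants balances participants, not therapists. Each therapist sits in one arm, so a difference between the two sets of therapists is indistinguishable from a difference between EMR and SOC. An analysis that treats participants as independent leaves that source of variation out of the standard error.

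The SAP's reason does not carry its conclusion. Inconsistent assignment rules out a strictly nested model. It does not rule out models in which a participant belongs to several therapists, clustering on the main therapist, or a sensitivity analysis. At stake is the Aim 1 test, which the SAP says could establish EMR as the gold-standard practice.

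**Working it through.** **Inputs from the documents.** Planned N is 252, taken as 126 per arm at 1:1 (Protocol opening summary: "improving functional and affective outcomes in 252 older adults admitted to SNFs for post-acute rehabilitation"). Effect size 0.4, power 80% and two-sided alpha 0.025 come from Protocol G1 and SAP Study Methods iii. The 5% analysis level comes from SAP Statistical Principles i.

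**Assumed inputs.** Therapists per arm, J = 4 to 15. The only count in the documents is four trained therapists in the pilot (Protocol B1). Therapist ICC for Barthel change = 0.01 to 0.05. The PT/OT pair of Protocol G4 is treated as one unit.

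**Step 1: the plan's own figure.** n per arm = 2(z₀.₉₈₇₅ + z₀.₈₀)²/d² = 2(2.241 + 0.842)²/0.16 = 118.8, so 119 per arm and N = 238. The t-test version gives 242 and ANCOVA with one covariate 241. The stated 252 is slightly larger, for a reason not given. Since 252/238 = 1.06 and 252/242 = 1.04, it leaves room for a design effect of only about 1.04 to 1.06 at the design alpha.

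**Step 2: what the SAP model covers.** With two time points, the BIC-chosen covariance describes two measurements on the same participant. It says nothing about two participants who share a therapist. With complete data the interaction is a difference in mean change, with standard error SD x √(2/126) under independence.

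**Step 3: one therapist unit per participant.** With m = 126/J, design effect DE = 1 + (m − 1) x ICC. The true standard error is the naive one times √DE, and the actual type I error is 2[1 − Φ(1.96/√DE)].

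| J per arm | m | ICC 0.01: DE, error | ICC 0.02: DE, error | ICC 0.05: DE, error |
|---|---|---|---|---|
| 4 | 31.5 | 1.305, 8.6% | 1.610, 12.2% | 2.525, 21.7% |
| 8 | 15.75 | 1.148, 6.7% | 1.295, 8.5% | 1.738, 13.7% |
| 15 | 8.4 | 1.074, 5.9% | 1.148, 6.7% | 1.370, 9.4% |

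**Step 4: shared therapists.** If each participant's therapist effect is the average over several therapists in the arm, the arm mean is still a weighted average of the same J therapist effects. With balanced use its therapist variance is (therapist variance)/J, however many therapists each participant sees. Simulation (20,000 runs per cell, naive test at 5%) agrees:

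| J per arm | Therapist variance share | 1 per participant | 2 per participant | 4 per participant |
|---|---|---|---|---|
| 6 | 0.05 | 17.8% | 17.4% | 17.6% |
| 12 | 0.02 | 7.5% | 7.4% | 7.2% |

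**Step 5: moderator tests.** MADRS, CIRS-G and SBT vary between participants of the same therapist, so a therapist effect on change largely cancels from the condition x moderator slope. In simulation (4,000 runs per cell; 4, 8 or 15 therapists per arm; ICC 0.01 and 0.05) the naive moderator test had error 4.3% to 5.6%. It rose to between 13.6% and about 15% only when the moderator's slope was also made to vary by therapist, with an assumed slope variance of 0.05.

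**Step 6: power for d = 0.4 at the SAP's 5% level.** Power = Φ(0.4/√(2DE/126) − 1.96), where 0.4/√(2/126) = 3.175.
- DE 1: Φ(3.175 − 1.96) = Φ(1.215) = 0.89.
- DE 1.295: Φ(3.175/1.138 − 1.96) = Φ(0.830) = 0.80.
- DE 1.738: Φ(3.175/1.318 − 1.96) = Φ(0.449) = 0.67.

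**The case against.** The strongest reply is that harm is not shown. Protocol G4 calls the correlation only possible, and the documents give neither an ICC nor a main-trial therapist count. At ICC zero the SAP analysis is right, and at the mild end of the table the error is 5.9% rather than 5%. This stands, and it makes the conclusion conditional. It does not justify removing, without a check, a safeguard the protocol thought necessary.

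Second, a reader might infer that all the Aim 2 moderator tests are anti-conservative too. The documents do not support that. The moderators are participant-level, and Step 5 shows error close to nominal unless slopes differ by therapist, which nothing in the documents indicates.

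Third, the fix may not be feasible in full. The SAP does not say what the inconsistency was; participants seeing changing therapists is plausible but unstated. No section shows therapist identity recorded for every session. Process measures are taken at a random 20% of sessions, and therapist adherence was tracked twice per participant. This stands, so fallbacks are needed. With few therapists, the variance components would also be imprecise.

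Fourth, the trial could claim only an effect for the therapists who took part. For that target the therapist-variance inflation does not apply. But the arm effect then cannot be separated from differences between the two sets of therapists, and the claim is narrower than the SAP's stated ambition.

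Fifth, sizing at 0.025 and testing at 5% leaves slack: power remains about 0.80 at a design effect of 1.295. A reader should not infer that the trial is necessarily underpowered.

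**Conclusion.** The concern holds in conditional form. The SAP withdrew a planned safeguard for its primary test, for a reason that excludes only strict nesting, and put nothing in its place. If Barthel change varies by therapist, the primary standard error is too small. Under the stated assumptions the nominal 5% becomes about 5.9% to 22%, and therapist sharing within an arm does not reduce it.

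The direction follows from therapists being confined to one arm. The size rests on assumed therapist numbers and ICCs, equal caseloads, and the planned 252, since the documents do not give the number randomised. It would be tempting to say flatly that the standard error is too small, or that the therapist sets are small. The documents establish neither.

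**What to change.** Replace the Note with a therapist-level analysis of the primary outcome. Specify it before the arm comparison is run, or label it post hoc if that has already happened.

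1. **Where therapist records allow:** fit a multiple-membership model weighted by each therapist's share of sessions, or cluster on the main PT and main OT. Use small-sample degrees of freedom, and report therapist counts per arm and the estimated ICC.
2. **Where they do not:** report the primary result with its standard error multiplied by √DE for ICC 0.01, 0.02 and 0.05, using the therapist count per arm or a stated range for it. With 8 per arm the multipliers are 1.07, 1.14 and 1.32.
3. **Scope of the claim:** state that, if therapist effects are neither modelled nor allowed for, the conclusion applies only to EMR as delivered by the participating therapists, and the arm effect cannot be separated from therapist differences. Note also that no variance adjustment removes a systematic difference arising because interested therapists took up EMR.

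The cost is SAP wording, retrieval of whatever assignment records exist, and modest analysis time; no participants or visits are added. The downside is a possibly wider interval, and an imprecise therapist variance if therapists are few.
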